## 1. VERSION HISTORY

**Table 1. Summary of Changes**

Version/ Date	Associated Protocol Amendment	Rationale	Specific Changes
2 03 Nov 2023	1 26 Mar 2021	Per protocol amendment 1	
 
Update whole document per protocol amendment 1 changes
 
Update use the latest SAP template
 
Add in details about the endpoints definitions in Section 3
 
Add in analyses details in Section 6, including COVID-19 analysis
 
Add in the analysis window for endpoints assessed less frequently in Appendix 1.1
 
Add in the Abbreviations in Appendix 2
 

1 23 Aug 2019	Original 28 Jun 2019	N/A	N/A

## 2. INTRODUCTION

This statistical analysis plan (SAP) provides the detailed methodology for summary and statistical analyses of the data collected in Study B3461077.

### 2.1. Modifications to the Analysis Plan Described in the Protocol

[Protocol section 9.4.1.2](#) Electrocardiogram Analyses states categories for QTcF as change from baseline are:  $\geq 30$  msec increase,  $\geq 60$  msec increase. A  $\geq 75$  msec increase category is added in [Section 6.2.3.2](#) as deemed clinical important.

[Protocol section 9.4.1.4](#) Other Safety Assessments states all clinical laboratory data will be summarized by frequency of events and mean changes from baseline. This change from baseline summary will not be done as considered clinical meaningless.

Protocol section 9.4.1.4 Other Safety Assessments states all vital sign measurements will be displayed in listings by participant with changes from baseline values included. This change from baseline values will not be listed as considered clinical meaningless.

[Protocol section 9.4.2](#) states PD endpoints will also be analyzed by TTR genotype. This subset analysis will only be done if sample sizes for both TTR wild-type and variant genotype subsets allowed.

### 2.2. Study Objectives, Endpoints, and Estimands

Type	Objective	Endpoint	Estimand
Safety	To characterize the safety profile of tafamidis once daily for the treatment of Chinese ATTR-CM patients in clinical practice	Incidence of treatment-emergent adverse events.	Not applicable

		Assessment of laboratory, ECG, Echocardiography, PE, Vital signs, BMI and mBMI at scheduled visits	
Efficacy	To characterize the descriptive efficacy of tafamidis once daily in Chinese ATTR-CM patients	Assessment of 6-MWT, NT-pro BNP, cardiac troponin I, and NYHA at scheduled visits	Not applicable
Pharmacodynamics	To characterize tafamidis pharmacodynamics (PD) in Chinese ATTR-CM patients	TTR stabilization and TTR concentration at baseline (pre dosing) on Day 1, at Months 1, 6, and 12 (or End of Treatment (EOT))	Not applicable
Quality of Life	To characterize the impact on quality of life of tafamidis once daily for the treatment of Chinese ATTR-CM patients	Kansas City Cardiomyopathy Questionnaire overall summary scores, EQ-5D-5L index scores and EQ-5D VAS scores, 12-Item Short Form Survey (SF-12) scores, at Day 1, Months 6, 12 (or EOT)	Not applicable
Pharmacokinetics	To characterize tafamidis pharmacokinetic (PK) in Chinese ATTR-CM patients	Plasma concentrations of tafamidis at Months 1, 6, and 12 (or EOT)	Not applicable

### 2.3. Study Design

This is a post approval commitment study conducted in China. It is a single-arm, open-label, multicenter study designed to obtain safety, efficacy, PK and PD data in ATTR-CM patients in China. Patients will be evaluated for study eligibility during the screening period between Days -45 and Day -1. At least 53 patients will be treated. All enrolled patients will receive tafamidis free acid (called as tafamidis in the texts hereafter) 61 mg soft capsules orally, once daily for 12 months, starting on Day 1, with scheduled visits at Baseline/Day 1, Month 1, 3, 6, 9 and 12. For the purpose of this study, 1 month is defined as 30 days.

### **3. ENDPOINTS AND BASELINE VARIABLES: DEFINITIONS AND CONVENTIONS**

#### **3.1. Primary Endpoint(s)**

- Incidence of treatment-emergent adverse events

An adverse event is any untoward medical occurrence in a patient or clinical study participant, temporally associated with the use of study intervention, whether or not considered related to the study intervention. All adverse events that start after the first dosing but before or on the last dose plus the lag time (28 days) will be flagged as treatment emergent adverse events. Adverse events will be coded according to the Medical Dictionary for Regulatory Activities (MedDRA).

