#### 8.3.1. Time Period and Frequency for Collecting AE and SAE Information

The time period for actively eliciting and collecting AEs and SAEs ("active collection period") for each participant begins from the time the participant provides informed consent, which is obtained before the participant's participation in the study (ie, before undergoing any study-related procedure and/or receiving study intervention), through and including a minimum of 28 calendar days, except as indicated below after the last administration of the study intervention.

Follow up by the investigator continues throughout and after the active collection period and until the AE or SAE or its sequelae resolve or stabilize at a level acceptable to the investigator and Pfizer concurs with that assessment.

For participants who are screen failures, the active collection period ends when screen failure status is determined.

If the participant withdraws from the study and also withdraws consent for the collection of future information, the active collection period ends when consent is withdrawn.

If a participant definitively discontinues or temporarily discontinues study intervention because of an AE or SAE, the AE or SAE must be recorded on the CRF and the SAE reported using the CT SAE Report Form.

Investigators are not obligated to actively seek AEs or SAEs after the participant has concluded study participation. However, if the investigator learns of any SAE, including a death, at any time after a participant has completed the study, and he/she considers the event to be reasonably related to the study intervention, the investigator must promptly report the SAE to Pfizer using the CT SAE Report Form.

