#### **9.2. Sample Size Determination**

In order to attain an 80% probability of observing at least 1 participant having an event for TEAEs with incidence rate of 3%, at least 53 participants need to be treated.

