###### 9.4.1.1. Treatment Emergent Adverse Event

All adverse events that start after the first dosing but before the last dose plus the lag time are treatment emergent adverse events. Adverse events will be coded according to the Medical Dictionary for Regulatory Activities (MedDRA).

The incidence of treatment-emergent adverse events will be tabulated by system organ class. The incidence of treatment-emergent adverse events will be displayed by severity and attribution. In addition, the incidence of serious adverse events and adverse events that cause withdrawal will be tabulated. All adverse events will be listed.

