##### **Events Meeting the AE Definition**

- Any abnormal laboratory test results (hematology, clinical chemistry, or urinalysis) or other safety assessments (eg, ECG, radiological scans, vital sign measurements), including those that worsen from baseline, considered clinically significant in the medical and scientific judgment of the investigator. Any abnormal laboratory test results that meet any of the conditions below must be recorded as an AE:
  - Is associated with accompanying symptoms.
  - Requires additional diagnostic testing or medical/surgical intervention.
  - Leads to a change in study dosing (outside of any protocol-specified dose adjustments) or discontinuation from the study, significant additional concomitant drug treatment, or other therapy.
- Exacerbation of a chronic or intermittent preexisting condition including either an increase in frequency and/or intensity of the condition.
- New conditions detected or diagnosed after study intervention administration even though it may have been present before the start of the study.
- Signs, symptoms, or the clinical sequelae of a suspected drug-drug interaction.
- Signs, symptoms, or the clinical sequelae of a suspected overdose of either study intervention or a concomitant medication. Overdose per se will not be reported as an AE/SAE unless it is an intentional overdose taken with possible suicidal/self-harming intent. Such overdoses should be reported regardless of sequelae.

The signs, symptoms, and/or clinical sequelae resulting from lack of efficacy will be reported as an AE or SAE if they fulfill the definition of an AE or SAE and meet the requirements as per [Section 8.3.8.1](#). Also, “lack of efficacy” or “failure of expected pharmacological action” constitutes an AE or SAE.

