#### **Follow-up of AEs and SAEs**

- The investigator is obligated to perform or arrange for the conduct of supplemental measurements and/or evaluations as medically indicated or as requested by the sponsor to elucidate the nature and/or causality of the AE or SAE as fully as possible. This may include additional laboratory tests or investigations, histopathological examinations, or consultation with other healthcare professionals.
- If a participant dies during participation in the study or during a recognized follow-up period, the investigator will provide Pfizer Safety with a copy of any postmortem findings including histopathology.
- New or updated information will be recorded in the originally completed CRF.
- The investigator will submit any updated SAE data to the sponsor within 24 hours of receipt of the information.

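### The TEAE definition goes by start date alone, so whether worsening of an adverse event already open at first dose counts in the primary endpoint depends on unstated CRF practice

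*SAP*

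**What the plan says.** TEAE incidence is the only primary endpoint (protocol section 3). The rule that decides which events enter it is given in two places:

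- SAP 3.1: "All adverse events that start after the first dosing but before or on the last dose plus the lag time (28 days") are flagged as treatment-emergent.
- Protocol 9.4.1.1: "All adverse events that start after the first dosing but before the last dose plus the lag time are treatment emergent adverse events".

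Both turn on the date the event started. SAP 2.1, which lists departures from the protocol's analysis, leaves this untouched.

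Three other provisions bear on the point:

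- Protocol 8.3.1 says that active collection "for each participant begins from the time the participant provides informed consent". The Schedule of Activities has adverse event monitoring at screening and baseline, and screening can begin at Day -45.
- Protocol 10.3.1 lists among events that are adverse events: "Exacerbation of a chronic or intermittent preexisting condition including either an increase in frequency and/or intensity of the condition".
- Protocol 10.3.3, on follow-up, says: "New or updated information will be recorded in the originally completed CRF".

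**The concern.** Collection starts before dosing, so a participant can reach the first dose with an adverse event already on the CRF and unresolved. If it then worsens on treatment, the TEAE flag depends on the date attached to the worsening. Updated on the existing entry, the event keeps a pre-dose start and is not flagged. Entered as a new event, it has a post-dose start and is flagged. The plan does not say which to do, and the follow-up instruction in 10.3.3 leans towards the first.

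Two sites could therefore record the same clinical course differently, and one participant would count in the primary endpoint while the other would not. In a single-arm study no control group is subject to the same counting rule, so an omission goes straight into the reported incidence. Worsening of an event under treatment is also something a safety study is meant to pick up.

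**Working it through.** **Inputs.** From protocol 9.2: "80% probability of observing at least 1 participant having an event", a TEAE incidence of 3%, and "at least 53 participants need to be treated". From the Schedule of Activities and SAP 2.3: screening from Day -45. From SAP 3.1 and protocol 9.4.1.1: the start-date rule. The documents give no figure for how many events are open at first dose or how many of those worsen.

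**Step 1: the plan's own figure.** The smallest n with 1 - (1 - p)^n ≥ 0.80 at p = 0.03 is ln(0.20)/ln(0.97) = 52.84, rounded up to 53. Check: 1 - 0.97^53 = 0.8010, and 1 - 0.97^52 = 0.7948. The 53 and the 80% both reproduce.

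**Step 2: apply the rule to each kind of worsening.**

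| Situation | Start date on record | Flagged as TEAE? |
|---|---|---|
| Medical-history condition worsens after first dose | After first dose (an adverse event in its own right under 10.3.1) | Yes |
| Adverse event opened in screening worsens after first dose, entered as a new record | After first dose | Yes |
| Same event, updated on its original entry | Before first dose | No |

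Only the third row is a gap. It needs four things together: onset between consent and first dose, no resolution by dosing, worsening on treatment, and recording as an update.

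**Step 3: where else such an event would be seen.** Protocol 9.4.1.1 and SAP 6.1.1 summarise serious adverse events without restricting them to treatment-emergent ones, and both list all adverse events. Worsening to serious would therefore appear in the SAE summary and the listings. Worsening from, say, mild to severe without becoming serious would appear only in the listings. It would be absent from TEAE incidence and from the TEAE severity tables by system organ class and preferred term.

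**Step 4: size.** One participant left out of a table row changes that row by 1/53 = 0.0189, or 1.9 percentage points, if the participant has no other qualifying event in the row. With more than 53 treated the change is smaller. It can only be downward, since the rule omits events and adds none.

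**Step 5: an illustration, not an estimate.** Suppose that a share f of participants with a given 3% event had it only in the third-row form. The counted rate would be 0.03 × (1 - f), and the chance of counting at least one among 53 would be 1 - (1 - 0.03(1 - f))^53:

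- f = 10%: rate 2.70%, probability 76.6%
- f = 20%: rate 2.40%, probability 72.4%
- f = 25%: rate 2.25%, probability 70.1%

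These values of f are assumptions with no basis in the documents. With a window of at most 45 days, the true share is probably small.

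**The case against.** The case for leaving the text alone is substantial.

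- **Worsening is already an adverse event.** Protocol 10.3.1 covers exacerbation, and the list of exclusions leaves out pre-existing conditions only where they do not worsen. Heart-failure symptoms present before consent are medical history, so their worsening on treatment counts. This stands, and it removes most of the clinically obvious cases.
- **The recording rule is silent, not adverse.** The follow-up sentence in 10.3.3 speaks of the CRF in general. It does not mention onset dates, or whether a rise in severity opens a new line. CRF completion instructions and the sponsor's reporting standards, which SAP 6.1.1 cites for summarising TEAEs, are not in the documents and may settle the matter. This also stands, as far as it goes. But SAP 3.1 states the flag itself without reference to those standards, and the primary endpoint should not rest on a convention that the plan leaves out.
- **Serious worsening is reported anyway.** This is correct, as shown above, but it does not restore the event to the primary endpoint, and it does not help with non-serious worsening.
- **The study is descriptive**, with no hypothesis or decision rule, so no conclusion turns on one participant. This is fair, and it limits the weight of the point.

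A reader might also infer that the detection probability of 80% is overstated. The documents do not support that. Protocol 9.2 takes 3% as the incidence of TEAEs and makes no claim about events outside the definition, so 1 - 0.97^53 remains 80.1%.

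**Conclusion.** The point holds as a limited weakness in the wording of the primary endpoint. The definition has no worsening clause, and for events open at first dose the plan leaves inclusion to unstated CRF practice. The effect, if any, is a downward error of 1.9 percentage points per missed participant at 53 treated. This rests on some sites updating the original entry, which the text suggests but does not state.

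A reader might infer that an event open at first dose which worsens on tafamidis can never reach the primary endpoint. That goes too far: it does reach it if entered as a new record, and worsening of medical-history conditions reaches it under Appendix 3. Nor is there support for a large bias, since neither document says how many participants enter with open events. The sample size needs no change. This is a cheap improvement worth making before database lock, not a defect that undermines the study.

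**What to change.** In SAP 3.1 and protocol 9.4.1.1, define a TEAE as an adverse event that starts after the first dose, or that starts before it and increases in severity or becomes serious after it, up to and including the last dose plus 28 days. Using the same sentence in both places also gives the protocol section the explicit 28-day lag and the inclusive end-point that only the SAP now has.

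The clause works only if the worsening can be dated. The CRF completion instructions should therefore require either a new record with its own onset date or a dated severity change on the existing record. Either will do, provided all sites use the same one. Because incidence counts participants, a second record for the same term does not count a participant twice.

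The cost is a change of wording in two documents, one line of CRF guidance and perhaps a few data queries on events open at first dose. Protocol section 9 requires major changes to the primary endpoint definition to be reflected in a protocol amendment, so the sponsor should decide whether this clarification qualifies. The number treated and the visit schedule stay as they are. The downside is that reported TEAE incidence may rise slightly.

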#### **3.2. Secondary Endpoint(s)**

Baseline for below endpoints is defined as the last measurement prior to dosing on Day 1 of the study. Change from baseline value is calculated by subtracting the baseline value from follow up visit value.

##### **3.2.1. Efficacy Endpoint(s)**

- Change from Baseline in the distance walked during 6 Minute Walk Test (6MWT)

6MWT is a kind of exercise test for patients with moderate to severe cardiopulmonary disease. It measures the longest distance a patient can walk on a straight course in 6 minutes.

6MWT will be conducted at baseline, Month 6 and 12.

- Change from Baseline in NT-proBNP concentration

Plasma amino-terminal pro-B-type natriuretic peptide (NT-proBNP) is a guideline-mandated biomarker in heart failure. Used as an inclusion criterion for therapeutic trials, NT-proBNP enriches trial populations and is a valid surrogate endpoint. NT-proBNP offers prognostic information independent of standard clinical predictors and refines risk stratification.

Blood sample collection will be performed at baseline, Month 6 and 12 for evaluation of NT-proBNP.

##### **3.2.2. Safety Endpoint(s)**

Not applicable.

##### **3.2.3. Pharmacodynamics (PD) Endpoints**

- TTR stabilization at Months 1, 6 and 12 (or EOT)

A responder in TTR stabilization is the participant who achieved TTR stabilization (ie, a participant who is TTR stabilized), defined as the patient whose percent stabilization  $\geq 32\%$ . The stabilization cut-off threshold was based on statistical modeling results: percent stabilization falling above 95% CI in placebo-treated participants with ATTR-CM in Phase 3 Study B3461028 (32%) were determined to be “stabilized”.

- TTR concentration at baseline (pre dosing) on Day 1, at Months 1, 6 and 12 (or EOT)

Refer to the separate Bioanalytical Plan as Appendix of Bioanalytical Report for calculation of TTR concentration and percent stabilization.

### **3.2.4. Quality of Life Endpoints**

All quality of life endpoints will be assessed at baseline, Month 6 and 12 (or EOT)

- Change from baseline in the Kansas City Cardiomyopathy Questionnaire Overall Summary scores (KCCQ-OS)

Changes from baseline in the KCCQ domain scores (Physical Limitation, Symptom Stability, Symptom Frequency, Symptom Burden, Total Symptom, Self-efficacy, Social Limitation, and Quality of Life) and Clinical Summary Score are also included as endpoints.

Total Symptom Score is calculated as the mean of Symptom Frequency and Symptom Burden Scores. Clinical Summary Score is calculated as the mean of Physical Limitation Symptom Frequency and Symptom Burden Scores. Overall Summary Score is calculated as the mean of Physical Limitation, Symptom Frequency, Symptom Burden, Quality of Life, and Social Limitation Scores.

- Change from baseline in Short-Form Survey 12 (SF-12, version 2, Acute) score

The 12-item Short Form Scale scores are summed into 2 scales: physical component summary score (PCS) and mental component summary score (MCS). In addition, 8 sub-scale scores are also included as endpoints: physical function (PF), role physical (RP), role emotional (RE), mental health (MH), bodily pain (BP), general health (GH), vitality (VT), and social function (SF). Higher scores indicate better quality of life.

- Change from baseline in EuroQol 5 Dimensions 5 Levels (EQ-5D-5L) index score and visual analog scale (VAS) scores

### **3.2.5. Pharmacokinetic (PK) Endpoints**

- Plasma concentrations of tafamidis at Month 1, 6 and 12

## **3.3. Other Safety Endpoints**

### **3.3.1. Laboratory Data**

- Incidence of laboratory abnormalities

Laboratory assessments include hematology, serum chemistry, urinalysis, coagulation and RBP tests performed at screening or baseline, Month 1, 6 and 12.

### **3.3.2. Electrocardiogram Data**

- Change from baseline in ECG measurements and incidence of electrocardiogram (ECG) abnormalities

12 lead ECG will be measured during screening, baseline, Month 1, 6 and 12. ECG parameters include heart rate, PR interval, QT interval, QTcF interval and QRS interval.

### 3.3.3. Echocardiograph Data

- Change from baseline in Echocardiography measurements and incidence of clinically significant changes in Echocardiography from baseline

Echocardiography parameters include end-diastolic interventricular septal wall thickness (mm), left ventricle posterior wall thickness (mm), left ventricular ejection fraction (%), left ventricular stroke volume (mL), fractional shortening (%), left atrial diameter, anterior-posterior (mm), left ventricular end systolic diameter (mm), left ventricular end systolic volume (mL), left ventricular end-diastolic diameter (mm), left ventricular end-diastolic volume (mL), left ventricular mass (g), and the ratio of peak velocity blood flow from gravity in early diastole (the E wave) to peak velocity flow in late diastole caused by atrial contraction (the A wave) (E/A).

Echocardiography will be measured at screening, Month 6 and 12.

### 3.3.4. Vital Signs

- Incidence of vital sign abnormalities

Vital sign measures include systolic blood pressure, diastolic blood pressure, pulse rate, respiratory rate, and body temperature. Vital signs will be measured at screening, baseline, Month 1, 6 and 12.

### 3.3.5. Physical Examination

- Incidence of clinical abnormality in physical examination

Full physical examination includes general appearance, head and neck, eyes, ears, skin, nose, throat, genitourinary, neurological, cardiovascular, abdomen, musculoskeletal, and respiratory and assessed at screening. Brief physical examination includes skin, lungs, cardiovascular, and abdomen. It will be assessed at baseline, Month 1, 6 and 12.

